Among patients with MF and advanced myeloid malignancies, side effects were predominantly GI. The most common AEs were diarrhea (81%), nausea (50%), fatigue (41%), vomiting (36%), anemia (26%), abdominal pain (23%), peripheral edema (24%), and constipation (20%). Grade 3/4 AEs were reported by 77% of patients. The most frequently occurring Grade 3/4 events in patients with MF were anemia (19%), thrombocytopenia (15%), fatigue (12%), and diarrhea (11%).

QTc Toxicities

CTI performed a post-hoc review of the phase 1-2 S*^BIO studies, SB1518-2007-001 and SB1518-2008-003, for potential cardiac toxicity, based upon a single case report of a QTc prolongation reported as a dose-limiting toxicity in the SB1518-2007-001 study. In these studies, ECGs were performed at baseline, periodically during the first 30 days of treatment, at termination, and as clinically indicated.

These studies have been completed. Clinical study reports are pending for Studies SB1518-2007-001 and -2008-003; thus, data are preliminary.

- Based on the identified DLT, CTI performed a full review of the patient profiles for all patients enrolled in these two studies. Review of these data identified the following observations:
- Nine patients across the studies had at least 1 reported QTc exceeding 500 ms, including the patient with the DLT. Of these 9 patients, 1 patient was receiving pacritinib at 150 mg per day, 1 at 450 mg per day, and the remaining 7 were receiving 400 mg per day. Baseline pre-pacritinib QTc intervals ranged from 441 to 491 ms. A majority (5) of the QTc prolongations were identified at the Day 29 time point, with the others identified on Days 1, 10, and 18.
 - At the time of the QTc events, 8 patients were on concomitant medications associated with QTc prolongation, including ondansetron (5 patients), levofloxacin (2 patients), venlafaxine (2 patients), and amiodarone, solifenacin, fluconazole, voriconazole, citalopram, cilostazol, and prochlorperazine in 1 patient each.
 - Pre-study cardiac history was also noted in 7 of the patients, including atrial fibrillation (3 patients), coronary artery disease (3 patients), myocardial infarction (3 patients), congestive heart failure (1 patient), heart murmur (2 patients), and syncope (2 patients).
- In addition to the DLT event, there were two QTc prolongations reported as non-serious AEs.

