13.0 REPORTING REQUIREMENTS

The Investigator or physician designee is responsible for verifying and providing source documentation for all adverse events and assigning the attribution for each event for all subjects enrolled on the trial. The PI or designee will be responsible for determining attribution for all events.

Grade 3 or 4 related and/or unexpected adverse events and protocol specific data will be entered into PDMS/CORE. PDMS/CORE will be used as the electronic case report form for this protocol.

Reporting Requirements

The descriptions and grading scales found in the revised NCI Common Terminology Criteria for Adverse Events (CTCAE) version 4.0 will be utilized for adverse event reporting. (<http://ctep.cancer.gov/reporting/ctc.html>).

Adverse event reporting will be as per the NCI criteria and the MDACC Leukemia Specific Adverse Event Recording and Reporting Guidelines.

Adverse event is any untoward medical occurrence that may present during treatment with a pharmaceutical product but which does not necessarily have a causal relationship with this treatment.

Adverse drug reaction is a response to a drug which is noxious and unintended and which occurs at doses normally used in man for prophylaxis, diagnosis, or therapy of disease or for the modification of physiologic function.

Assessing causal connections between agents and disease is fundamental to the understanding of adverse drug reactions. In general, a drug may be considered a contributory cause of an adverse event if, had the drug not been administered, 1) the event would not have happened at all, 2) the event would have occurred later than it actually did, or 3) the event would have been less severe.

Adverse Events (AEs) will be evaluated according to the most current version of the Pacritnib Investigator Brochure for expectedness. The current CTC version will be used to assess and grade AE severity. Only unexpected AEs will be recorded in the Case Report Form (CRF). Expected events during leukemia therapy are:

1. *Myelosuppression related events (due to disease or leukemia therapy)*
 - a. *febrile or infection episodes not requiring management in the intensive care unit*
 - b. *epistaxis or bleeding except for catastrophic CNS or pulmonary hemorrhage*
 - c. *anemia, neutropenia, lymphopenia, thrombocytopenia, leukopenia, leukocytosis*
2. *Disease related events*
 - a. *symptoms associated with anemia*
 - i. *fatigue*
 - ii. *weakness*

- iii. *shortness of breath*

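### Section 13.0 gives two conflicting rules for which adverse events enter the electronic CRF, and one of them omits expected drug-related non-hematological grade 3/4 events that Tables 11 and 14 count

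*Combined protocol and SAP*

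**What the plan says.** Section 13.0 contains both rules. The first is "Grade 3 or 4 related and/or unexpected adverse events and protocol specific data will be entered into PDMS/CORE", followed by "PDMS/CORE will be used as the electronic case report form for this protocol". The second, placed after the definitions of adverse event and adverse drug reaction, is "Only unexpected AEs will be recorded in the Case Report Form (CRF".

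Expectedness is judged against the Investigator Brochure, and the section also prints a list of expected events. That list includes non-hematological items: "febrile or infection episodes not requiring management in the intensive care unit", "symptoms associated with anemia" (fatigue, weakness, shortness of breath), and pain in bone, joint or muscle.

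In Section 12.0 (Statistical Considerations), Tables 11 and 14 stop accrual on the number of drug-related non-hematological grade 3/4 toxicities and make no exception for expected ones. The Statistical Analysis Plan paragraph of the same section promises frequency tables of toxicity by type, severity and attribution.

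**The concern.** Both rules govern one record, because PDMS/CORE is the CRF. An event that is expected, non-serious, not a laboratory value, non-hematological, grade 3/4 and drug-related enters that record under the first rule and is excluded by the second. The stopping rules count exactly this kind of event.

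If staff followed the second rule and the monitoring counts were drawn from the CRF, the toxicity rule would work on too few events and the reported grade 3/4 rate would be too low. Safety and tolerability are part of the study objective in Section 1.0, so the ambiguity touches a main result.

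**Working it through.** **1. The two rules side by side** (non-hematological, grade 3/4, drug-related, non-serious, not a laboratory value)

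| Event | PDMS/CORE sentence | Later CRF sentence | Tables 11 and 14 |
|---|---|---|---|
| Unexpected | recorded | recorded | counted |
| Expected | recorded | not recorded | counted |

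The and/or in the first sentence is loose, but on any reading it admits related events that are expected. The word only in the second does not.

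**2. Can an event be both expected and drug-related?** Yes. Section 13.0 says "a drug may be considered a contributory cause of an adverse event if, had the drug not been administered", the event would not have happened, would have come later, or would have been less severe. A listed event made worse by the drug therefore qualifies. Candidates from the printed list, when attributed to the drug, are infection managed outside intensive care, bone, joint or muscle pain, and anemia-associated fatigue. Diarrhea and nausea, which Section 6.0 describes as dose-related, are not on the printed list. They join the class only if the Investigator Brochure, which was not available, lists them as expected.

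**3. Reproducing the plan's boundaries.** For x toxicities in n patients, stop at the smallest x with P(p > limit | Beta(a + x, b + n − x)) above the cut-off, for n = 5, 10, ..., 35.

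- Part 1: Beta(0.3, 1.7), limit 0.15, cut-off 0.975. At n = 5, x = 3 gives 0.973 (continue) and x = 4 gives 0.997 (stop). All looks: 4, 5, 6, 7, 8, 10, 11, as in Table 11.
- Part 2: Beta(0.6, 1.4), limit 0.30, cut-off 0.95. All looks: 4, 6, 8, 10, 12, 14, 16, as in Table 14.

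**4. Effect of a small loss on Table 11.** The stopping probability comes from exact binomial recursion in cohorts of 5, removing paths that have crossed a boundary. Recorded rate = true rate − 0.04. The 4 points are an assumption with no source in the documents; over 35 patients they amount to 0.04 × 35 = 1.4 patients. The calculation further assumes that these patients have no other countable toxicity and that the count is taken from the CRF alone.

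| True rate | P(stop), all recorded | Recorded rate | P(stop), 4 points lost |
|---|---|---|---|
| 30% | 0.6118 | 26% | 0.4189 |
| 40% | 0.9257 | 36% | 0.8383 |

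These figures are for the toxicity rule alone and come from the printed boundaries. Table 13 combines toxicity with futility. At 40% toxicity and 15% ORR the same recursion, with a futility stopping probability of 0.1076, gives 1 − (1 − 0.9257)(1 − 0.1076) = 0.9337, against 0.9529 printed. That difference is not explained here, and the comparison above does not use Table 13. In Part 2 the combined figure at 50% toxicity and 30% ORR is 0.8484, as printed in Table 16.

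**The case against.** Much in the documents limits the loss.

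- The PDMS/CORE sentence, if followed, captures every event in question.
- Section 13.0 requires source documentation and attribution for all adverse events. Serious events go to the IND Office whether expected or not.
- Grade 3/4 chemistry peaks are entered in the CRF although many chemistry abnormalities are on the expected list, so the protocol does not itself treat the restriction to unexpected events as absolute.
- Table 4 in Section 5.0 makes investigators act on clinically significant related non-hematological grade 3/4 toxicity, so most such events should be noticed as they occur.
- Section 13.0 adds "Adverse event reporting will be as per the NCI criteria and the MDACC Leukemia Specific Adverse Event Recording and Reporting Guidelines". Those guidelines were not available and may settle the matter.

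All of this stands. It shows that the events would probably be known somewhere. It does not show that a non-serious, non-laboratory, expected event reaches the CRF, and no section names the source of the monitoring counts.

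A reader might go further and infer that grade 3/4 fatigue will be lost wholesale, since Section 2.3 reports: "The most frequently occurring Grade 3/4 events in patients with MF were anemia (19%), thrombocytopenia (15%), fatigue (12%), and diarrhea (11"%). The documents do not support that. The 12% covers any attribution, in another disease. The printed list puts fatigue under disease-related events, as a symptom of anemia, and the stopping tables count it only if it is attributed to the drug. Related fatigue of all grades was 4/31, 5/20 and 7/34 in three of the four myeloid groups. In the fourth (n = 43) fatigue is absent from the most common related events, the least frequent of which had n = 5. If fatigue there was at most 5, the total is at most (4 + 5 + 7 + 5)/128 = 21/128, or 16%. A 12-point loss is about 0.12 × 128 = 15 patients, so roughly 15/21 = 71% of all related fatigue would have to be grade 3/4, non-serious and anemia-associated.

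A reader might also infer that the stopping rule is already compromised. That would require the CRF to be the only source of the counts, which the plan does not say.

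**Conclusion.** The contradiction in Section 13.0 is real and stands in the current text. Its consequence is conditional: counts fall short only if the later sentence is followed, the event is expected and non-serious, and monitoring relies on the CRF. If any of these fails, nothing is lost from the monitoring.

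Under those conditions even a small loss matters. An assumed 4 points lowers the chance that the Table 11 toxicity rule stops Part 1 by about 19 percentage points at a true rate of 30% (0.6118 − 0.4189) and about 9 at 40% (0.9257 − 0.8383). These figures show sensitivity and are not an estimate of what will happen. Table 14 counts the same kind of event and is open to the same shortfall. The point should be fixed because a stated rule can produce a wrong count and the repair is cheap, but it sits at the lower end of that category.

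**What to change.** **Section 13.0.** Replace the sentence limiting the CRF to unexpected events with: *All grade 3 or 4 drug-related AEs, whether expected or unexpected, and all unexpected AEs will be recorded in PDMS/CORE with grade and attribution; the expected-event list does not exempt a drug-related non-hematological grade 3/4 AE.* Keep the existing exclusion of abnormal hematologic values, and check the wording against the institutional recording guidelines that the section cites.

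**Section 12.0 (Statistical Considerations).** State that the counts for Tables 11 and 14 include every drug-related non-hematological grade 3/4 toxicity, regardless of expectedness and from any source (CRF, source documents or SAE reports). This avoids tying the stopping rule to CRF entries alone.

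**Statistical Analysis Plan paragraph.** State that the toxicity tables cover the AEs recorded under this rule, so that expected lower-grade events are not implied to be complete.

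The cost is a short clarifying amendment and slightly more data entry. Adverse events are already assessed at each clinic visit (Section 8.0), and attribution is already required for each one.
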